#### Hypothesis for Aim 1:

1.1 – After starting Omegaven® on PN, the rate of fatty acid deficiencies and imbalances will be as low as before Omegaven®. Also, the rate of triglyceride events > 400 mg/dL with Omegaven® will be similar to that seen with PN administered with soy oil IFE (conventional emulsion, i.e., Intralipid®).

1.2 – PN containing Omegaven® will be safe for patients with respect to the risk of unexpected bleeding, coagulopathies, and other adverse events.

[name], Department of Surgery, Children's Hospital & Medical Center  
[name], Department of Surgery, Children's Hospital & Medical Center  
[name], Pediatric Research Office, Dept. of Pediatrics, UNMC  
[name], Department of Biostatistics, College of Public Health, UNMC

1.3 – PN containing Omegaven® will promote more short-term growth and development than conventional fat emulsions.

2. To determine if established PN associated liver disease can be reversed or its progression halted by using a parenteral fat emulsion prepared from fish oil as measured by normalization of serum levels of hepatic enzymes and bilirubin.

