### *Analysis of Safety and Tolerability of Omegaven®*

All primary safety and tolerability analyses will be based on descriptive statistics. In secondary analyses, we will also assess the statistical significance of differences. The period receiving Omegaven® will start 30 days after beginning PN with Omegaven® for the main analysis. Outcomes measured in the Omegaven® will be described for a period starting 30 days after baseline.

Primary outcomes measured will include whether the triene/tetraene ratio was ever  $> 0.2$  during the intervention period and whether the INR was ever  $> 2$ . Secondary outcomes measured will include platelets, prothrombin time (PT), partial thromboplastin time (PTT), and other components of the fatty acid profile. Analysis of all categorical outcomes will be based on proportions and of all continuous outcomes will be based on means or medians of the individual mean, maximum or minimum values, as appropriate, during the respective follow-up period. Comparisons between periods (pre and post-treatment) will be performed based on paired tests, parametric or non-parametric, as appropriate. We will also explore trends over time (e.g., decreasing for INR and increasing for pre-albumin) and estimate p-values via regression models using generalized estimating equations or random effects to account for within subject correlations. When describing outcomes over time, we will explore the effect of predictors of poor hepatic outcomes, such as use of antifungal agents (e.g., amphotericin) and antidiarrheal agents (e.g., loperamide), on potential spikes.

[name], Department of Surgery, Children's Hospital & Medical Center  
[name], Department of Surgery, Children's Hospital & Medical Center  
[name], Pediatric Research Office, Dept. of Pediatrics, UNMC  
[name], Department of Biostatistics, College of Public Health, UNMC

We will also evaluate nutritional outcomes including difference in weight-for- age Z-scores and height-for-age Z-scores from baseline to the moment in which the child starts enteral feeding and to the moment in which the child receives less than 10% of their calories from PN. Using linear regression, we will explore adjustment for baseline alternative predictors of interest. Trends over time in Z-scores will also be explored using regression with repeated measure methods.

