#### *Statistical Power and Sample Considerations*

The number of subjects included in the study will be based on a compassionate use protocol and not on study power considerations. The primary safety analysis will be descriptive and not based on statistical significance. However, in Table 4 we outline power to detect several differences in the frequency of adverse events, assuming 20, 25, or 30 patients, diverse proportion of subjects with adverse event in either treatment period and not with the adverse event in either treatment period and not with the adverse event in the other (proportion of discordant pairs), for a two-sided 5% significance level McNemar's tests.

For lower proportions of discordant pairs, we would generally attain close to 80% power in McNemar's test. Even for higher proportions of discordant pairs, assuming the high differences between before and after treatment that we expect to observe, e.g., 50% or more, 80% power can be attained in McNemar's test (Table 4).

Table 4—Power to detect varying differences in proportions before and after treatment with Omegaven® in a McNemar's test. All calculations based on an alpha significance level of 0.05

Difference between proportions	Proportion of discordant pairs	McNemar's Test		
		Sample Size		
		20	25	30
30%	40%	59%	72%	81%
	60%	44%	55%	63%
50%	60%	92%	97%	99%
	80%	79%	88%	93%
80%	85%	>99%	>99%	>99%
	95%	>99%	>99%	>99%

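### Table 4 is labelled two-sided 5% McNemar power, but its 12 numeric cells are one-sided 5% values

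*Protocol*

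**What the plan says.** In the protocol's Statistical Power and Sample Considerations, Table 4 is introduced with the words "in Table 4 we outline power to detect several differences in the frequency of adverse events", "assuming 20, 25, or 30 patients" and several proportions of discordant pairs, "for a two-sided 5% significance level McNemar's tests". The table caption gives the level but no side: "All calculations based on an alpha significance level of 0.05". The variant of McNemar's test is not named.

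Two conclusions are drawn from the table. At lower discordance, power is said to be generally near 80%. At higher discordance, "assuming the high differences between before and after treatment that we expect to observe, e.g., 50% or more, 80% power can be attained".

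The same section says that enrolment follows compassionate use rather than power, and that the primary safety analysis is descriptive. The tests that the table describes are planned under Analysis of Safety and Tolerability of Omegaven®: "In secondary analyses, we will also assess the statistical significance of differences" and "Comparisons between periods (pre and post-treatment) will be performed based on paired tests".

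**The concern.** Each cell of Table 4 is fixed by the number of patients, the difference, the proportion of discordant pairs and the significance level, all of which are printed. The figures can therefore be checked without outside information, and they look too high for a two-sided test at these sample sizes.

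The risk is one of interpretation. A reader who takes Table 4 at face value would credit the pre/post safety comparisons with more power than they have, and could read a non-significant difference as more reassuring than it is.

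A side point: the outcome behind the expected difference of 50 points or more is not named. If it were the triene/tetraene ratio, it would sit badly with hypothesis 1.1, that "the rate of fatty acid deficiencies and imbalances will be as low as before Omegaven". If it is another safety outcome, there is no conflict. The verdict does not depend on this.

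**Working it through.** **Inputs (Table 4 and its introduction).** n = 20, 25, 30 pairs; difference d = 30%, 50%, 80%; discordant proportion ψ as printed for each row; α = 0.05.

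**Method.** The number of discordant pairs is m ~ Binomial(n, ψ). Given m, the number in the favoured direction is x ~ Binomial(m, p), with p = (ψ + d)/(2ψ). Power is the sum, over all m and x at which the test rejects, of P(m) × P(x | m).

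- Exact one-sided: reject if P(X ≥ x | m, ½) ≤ 0.05.
- Exact two-sided: reject if twice the smaller tail is ≤ 0.05.
- Continuity-corrected one-sided: reject if (2x − m − 1)/√m ≥ 1.645.

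**Step 1: reproduce the printed figures.** Power in % for n = 20/25/30:

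| d / ψ | Printed | One-sided 5%, exact | Two-sided 5%, exact |
|---|---|---|---|
| 30% / 40% | 59/72/81 | 58.51/71.63/81.45 | 45.49/60.20/71.31 |
| 30% / 60% | 44/55/63 | 43.69/54.61/63.39 | 30.57/40.97/50.18 |
| 50% / 60% | 92/97/99 | 91.92/97.16/99.01 | 85.49/93.69/97.55 |
| 50% / 80% | 79/88/93 | 79.29/87.95/93.00 | 68.37/79.14/86.63 |

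The one-sided column rounds to the printed value in 12 of 12 cells, with a largest gap of 0.49 point. The one-sided continuity-corrected test gives the same values to two decimals, so the table cannot show which of the two was used. One-sided mid-p and one-sided uncorrected tests match only 1 of 12 cells each. The two-sided exact column matches none.

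**Step 2: where the difference arises.** Take n = 20, d = 30%, ψ = 40%, so p = 0.70/0.80 = 0.875. With m = 8 discordant pairs, P(X ≥ 7 | ½) = 9/256 = 0.035. A one-sided test therefore rejects at 7 of 8. The two-sided p-value is 0.070, so a two-sided test needs 8 of 8. The conditional power is 73.6% against 34.4%. With m = 5, the one-sided test can reject at 5 of 5 (1/32 = 0.031), whereas the two-sided test cannot reject at all (0.0625). Summing over m gives 58.51% and 45.49%.

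**Step 3: could another two-sided variant have been used?** With z = 1.960, Connor's formula is Φ[(d√n − z√ψ)/√(ψ − d²)] and Miettinen's is Φ[(d√(nψ) − zψ)/√(ψ² − ¼d²(3 + ψ))]. The other rows are enumerated as above.

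| Two-sided 5% variant | 30/40 | 30/60 | 50/60 | 50/80 | Cells matched |
|---|---|---|---|---|---|
| Exact | 45.49/60.20/71.31 | 30.57/40.97/50.18 | 85.49/93.69/97.55 | 68.37/79.14/86.63 | 0 |
| Continuity-corrected | 45.49/60.17/71.04 | 30.29/38.32/47.18 | 85.45/93.25/97.05 | 64.31/77.91/86.59 | 0 |
| Mid-p | 58.29/70.51/79.39 | 39.46/50.03/57.92 | 90.77/96.28/98.62 | 76.17/83.98/90.21 | 1 |
| Uncorrected | 60.34/70.92/79.46 | 39.47/50.15/59.39 | 90.79/96.28/98.66 | 76.17/85.93/91.67 | 1 |
| Connor | 57.27/68.00/76.57 | 40.24/48.98/56.95 | 88.75/95.15/98.04 | 74.26/84.31/90.81 | 0 |
| Miettinen | 58.84/71.56/81.15 | 39.79/48.94/57.27 | 93.49/98.08/99.50 | 75.21/85.38/91.77 | 4 |

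In the 30/60 and 50/80 rows the printed power exceeds all six variants, by at least 3.6 to 4.9 points and 1.2 to 2.8 points respectively. In the 30/40 and 50/60 rows the printed values fall, after rounding, within the range of the large-sample variants.

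An unpooled-variance (Wald) formula, which is not McNemar's statistic, was also run. It gives values above the printed ones throughout (46.76/55.59/63.34 in the 30/60 row, for example) and matches 1 cell.

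**Step 4: the 80% rows.** Exact two-sided power is 99.92/99.99/100.0 (ψ = 85%) and 99.04/99.81/99.97 (ψ = 95%), so these six cells are essentially unaffected. The lowest value among the six variants is about 98.8%, for the continuity-corrected test at ψ = 95% and n = 20.

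**Step 5: the two conclusions.** For d = 50% and ψ = 80%, two-sided power reaches 80% from n = 26 (exact), 27 (continuity-corrected), 23 (mid-p) or 22 (uncorrected). With the exact test only the n = 30 column qualifies. For d = 30% and ψ = 40%, exact two-sided power peaks at 71%, not 81%.

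**The case against.** The strongest reply is that nothing in the study hangs on Table 4. The number of patients is not derived from it, the primary safety analysis is descriptive, and the tests it describes are secondary. That is correct, and it limits the weight of the point.

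A second reply is that the main power claim survives. For a 50-point difference, 80% power is attained at n = 30 under every two-sided variant in the working, the lowest value being 86.6% in the 80%-discordance row. That also stands. The sentence is true as written, though with less margin than the table shows.

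A third reply is that the size of the error depends on the comparator, since the protocol names no variant. Against the uncorrected two-sided test the largest overstatement is 4.9 points, and one cell (30/40, n = 20) is slightly understated: 59% printed against 60.3%. This is fair and affects how the gap should be reported. It does not rescue the label, because no two-sided variant tried reproduces the table while one one-sided calculation reproduces every numeric cell.

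**Conclusion.** The point holds. The 12 numeric cells of Table 4 are one-sided 5% (equivalently two-sided 10%) McNemar power, presented as two-sided 5%.

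Against the exact two-sided test the overstatement is 10 to 14 points (30/40 row), 13 to 14 (30/60), 1 to 7 (50/60) and 6 to 11 (50/80). The exact test is the natural comparator because it is one of the two variants that match one-sided, but the choice is an assumption. Under large-sample variants the gap falls to about 6 points or less, and in a few cells it vanishes or reverses.

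The calculation assumes independent pairs and the printed discordance proportions, and it uses no outside figure. The effect is confined to the power statement for the secondary pre/post tests. Sample size and primary analysis are untouched. The correction should be made, but nothing in the conduct of the study waits on it.

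**What to change.** Recompute Table 4 at two-sided 5%, state the side in the caption as well as the text, and name the test variant. Then rewrite the two sentences drawn from the table. With the exact test, over n = 20 to 30, they would report:

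- 30-point difference: 45–71% power at 40% discordance and 31–50% at 60%.
- 50-point difference: 85–98% at 60% discordance and 68–87% at 80%, where 80% power is reached only at n = 30 among the tabulated sizes.
- 80-point difference: 99% or more.

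Relabelling the table and text as one-sided 5% would also remove the contradiction. It is second best, because the protocol describes its tests as two-sided and plans no one-sided test. While editing, name the outcomes to which the expected difference of 50 points or more applies.

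The cost is one table and a few sentences, with no extra patients and no change to the analyses. The stated power becomes less favourable.

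### The statement that lower discordance generally gives close to 80% power overstates Table 4 for a 30% difference with 40% discordant pairs, where the printed power is 59% at n = 20 and 72% at n = 25

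*Protocol*

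**What the plan says.** The protocol section on statistical power and sample considerations states that enrolment "will be based on a compassionate use protocol and not on study power considerations". It then offers Table 4 as a guide to what a paired before/after comparison could detect, "assuming 20, 25, or 30 patients" and "for a two-sided 5% significance level McNemar's tests". Two sentences interpret the table:

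- Lower discordance: "For lower proportions of discordant pairs, we would generally attain close to 80% power". No size of difference is attached.
- Higher discordance: "assuming the high differences between before and after treatment that we expect to observe, e.g., 50% or more, 80% power can be attained". This one is limited to large differences.

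Table 4 then lists two discordance levels for each of three differences (30%, 50%, 80%). Its caption says "All calculations based on an alpha significance level of 0.05" and does not state sidedness.

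**The concern.** A reader of the first sentence would take it to cover every difference in the table, including 30%. The condition on the size of the difference appears only in the following sentence, which begins by contrasting higher discordance with the case just described. The lower-discordance row for a 30% difference nevertheless falls well short of 80% at two of the three sample sizes.

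What is at stake is how a null result is read. The protocol's section on safety and tolerability makes the primary safety analyses descriptive, but plans significance assessment in secondary analyses and paired tests between the pre- and post-treatment periods. The binary primary safety outcomes are a triene/tetraene ratio ever above 0.2 and an INR ever above 2. If such a test on about 20 patients is non-significant, the sentence suggests a miss probability of roughly 20% for a real change. For a 30% difference with 40% discordance, the printed table implies 100% − 59% = 41%.

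**Working it through.** **Step 1. Printed cells against the sentence.** Taking the lower discordance level within each difference, Table 4 prints:

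| Difference | Discordant pairs | n = 20 | n = 25 | n = 30 |
|---|---|---|---|---|
| 30% | 40% | 59% | 72% | 81% |
| 50% | 60% | 92% | 97% | 99% |
| 80% | 85% | >99% | >99% | >99% |

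Seven of the nine cells are 81% or more. The two below 80% are both in the 30%/40% row: 80 − 59 = 21 points short at n = 20, and 80 − 72 = 8 points short at n = 25.

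The higher-discordance rows are 44/55/63% (30%/60%), 79/88/93% (50%/80%) and >99% throughout (80%/95%).

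**Step 2. Reproducing the printed row.** Inputs from the protocol: difference d = 0.30, discordance π = 0.40, n = 20, 25, 30, α = 0.05.

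- The two discordant cell probabilities are (π + d)/2 = 0.35 and (π − d)/2 = 0.05.
- Given m discordant pairs, the count in the favoured direction is binomial with q = 0.35/0.40 = 0.875; under the null it is binomial with 0.5.
- Exact unconditional power = Σ over m of Bin(m; n, 0.40) × Pr(the binomial test on m pairs rejects | q = 0.875).

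| Method, 30%/40% row | n = 20 | n = 25 | n = 30 |
|---|---|---|---|
| Printed | 59% | 72% | 81% |
| Exact, one-sided 5% | 58.5% | 71.6% | 81.4% |
| Miettinen approximation, two-sided 5% | 58.8% | 71.6% | 81.1% |
| Connor approximation, two-sided 5% | 57.3% | 68.0% | 76.6% |
| Exact, two-sided 5% | 45.5% | 60.2% | 71.3% |

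The Connor figure at n = 20, for example, is Φ[(d√n − 1.96√π)/√(π − d²)] = Φ[(1.342 − 1.240)/0.557] = Φ(0.183) = 57.3%.

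So the printed row is reproducible and the 59% and 72% are not misprints. No method in this table brings n = 20 or n = 25 to 80%.

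**Step 3. Which level the table uses.** Two methods reproduce this row, so the row alone does not settle sidedness. Across the twelve numeric cells of the 30% and 50% rows, the one-sided exact test at 5% matches all twelve. The best two-sided variants tried match seven, and the two-sided exact test matches one. The text declares two-sided tests. That mismatch is a separate matter, but it determines which figures a corrected sentence should carry.

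**The case against.** The sentence is hedged twice, by its adverb and by speaking of being near 80% rather than at it. Seven of nine lower-discordance cells are 81% or more, and power above 80% does not count against it. The protocol also says that it expects differences of 50% or more, so the 30% row is not its planning case, and the figures are printed directly below the text. All of this stands, and it confines the point to one row. It does not rescue that row: 59% is not close to 80%, 72% is arguable at best, and nothing in the sentence excludes a 30% difference.

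A reader might infer three stronger things that the document does not support:

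- **That a promised power is missed.** No power target is set. Enrolment follows compassionate use and the primary safety analysis is descriptive.
- **That no listed sample size reaches 80% in this row.** This is true of the exact two-sided test (71.3% at n = 30) and of the Connor approximation (76.6%), but not of the two-sided Miettinen approximation (81.1%) or of the table as printed (81%). The protocol does not name its method.
- **That 80% at all three sizes is obtained only with differences of 50% or more at the lower discordance.** The 80%/95% row is a higher-discordance row and prints >99% throughout.

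The word *lower* is itself loose, because 60% is the higher level for a 30% difference and the lower level for a 50% difference. Read as absolute discordance, the sentence would also take in the 44/55/63% row. The within-difference reading used here is the one more favourable to the protocol.

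**Conclusion.** The point holds as a wording error limited to one row. For a 30% difference with 40% discordant pairs, the sentence overstates the protocol's own table by 21 points at n = 20 and 8 points at n = 25; only n = 30 agrees with it. The other two lower-discordance rows exceed 80% at every size.

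This conclusion needs only the printed cells and does not depend on sidedness or on the McNemar method. The size of the overstatement does: at the declared two-sided 5% level it is larger with an exact test (about 46/60/71%) and close to that printed with the Miettinen approximation. Enrolment, conduct and the descriptive primary safety analysis are unaffected. What is affected is how much reassurance a non-significant secondary paired test may give.

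**What to change.** Replace the sentence with the power for a 30% difference and 40% discordance at n = 20, 25 and 30, and limit the 80% statement to where the table supports it. On the figures as printed, that is:

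- 30%/40%: n = 30 only
- 30%/60%: at no listed size (44/55/63%)
- 50%/60%: all three sizes
- 50%/80%: n = 25 and n = 30, with 79% at n = 20
- 80%/85% and 80%/95%: all three sizes

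Before the figures are copied over, recompute Table 4 at the declared two-sided 5% level and name the McNemar method in the caption. With the exact two-sided test the 30%/40% row becomes about 46/60/71%, and the list above must be redrawn from the new table; the 50%/80% row, for instance, becomes about 68/79/87%.

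The cost is a sentence or two of text and a short recalculation. Enrolment does not change; the stated power becomes less favourable.

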#### **DATA AND SAFETY MONITORING PLAN**

Patients will be monitored while receiving Omegaven® treatment to observe for signs of Omegaven® toxicity. At the start of Omegaven® therapy, patients will be monitored closely during and shortly after initial Omegaven® administration to observe for signs of allergic reaction and anaphylaxis. In the event the patient demonstrated signs or symptoms of allergic reaction, the Omegaven® will be discontinued and the PI and attending physician will be notified.

Selected safety labs will be evaluated by attending staff and the Study Investigators for both clinical and research purposes. Blood samples will be taken prior to the start of therapy (baseline), and thereafter in accordance with the scheduled represented in the tables below.

#### **Reversal Study Lab Schedule:**

Patient Status	Parameter	Tests to be Performed	Frequency
Inpatient/receiving Omegaven®	Direct bilirubin $\geq$ 2 mg/dL	PN profile, AST, GGT, CRP, lipid Panel, PT, PTT, INR, fibrinogen, EFA Panel	Weekly
	Direct bilirubin $<$ 2 mg/dL	PN profile PN profile, AST, GGT, CRP, PT, PTT, INR, fibrinogen, EFA panel, lipid panel	Weekly Monthly

[name], Department of Surgery, Children's Hospital & Medical Center  
 [name], Department of Surgery, Children's Hospital & Medical Center  
 [name], Pediatric Research Office, Dept. of Pediatrics, UNMC  
 [name], Department of Biostatistics, College of Public Health, UNMC

Inpatient/off Omegaven®	Direct bilirubin $\geq$ 2 mg/dL	PN profile	Weekly
	Direct bilirubin < 2 mg/dL	PN profile, AST, GGT, CRP, lipid Panel, PT, PTT, INR, fibrinogen, EFA Panel	one complete set of post-Omegaven labs
Outpatient/on Omegaven®	Direct bilirubin $\geq$ 2 mg/dL	PN profile, AST, GGT, CRP, lipid Panel, PT, PTT, INR, fibrinogen, EFA Panel	Weekly
	Direct bilirubin < 2mg/dL	PN profile, AST, GGT, CRP, lipid Panel, PT, PTT, INR, fibrinogen, EFA Panel	Monthly until off Omegaven and at least 1 direct serum bilirubin < 2 mg/dL

#### **Safety Labs Schedule:**

Lab Name	Schedule*
Serum triglycerides	At baseline, weekly for 4 weeks, monthly thereafter
Coagulation labs	At baseline, weekly until direct bilirubin is < 2mg/dL, monthly thereafter
Fatty acid profile	At baseline, monthly thereafter

\*minimum requirements, may be performed more frequently for routine clinical care

If under the discretion of the principal investigator the patient is able to return home and receive Omegaven®, the patient is required to return to Children's Hospital & Medical Center every 2 months or other mutually agreed upon schedule for evaluation and follow up. The Principle Investigator also requires for arrangements to be made through the patient's home health care agency for the required weekly or monthly blood draws the patient will need while at home in order to remain on Omegaven®. The lab results then must be faxed to Children's Hospital & Medical Center in a timely manner. Additionally, measures will be taken to decrease the chance of administration errors when Omegaven® is given in the home. Families will be provided with a letter outlining strategies for reducing medication administration errors, such as independent double-checks.

Dose reduction will occur if there is evidence of lipid intolerance (serum triglycerides  $>$  200mg/dL) or evidence of bleeding. Growth indices include weight, length, and head circumference will also be monitored.

Other standard care laboratory results will be captured for the Omegaven® protocol. These are listed along with the standard schedule in Table 3.

The frequency of laboratory monitoring may be reduced to monthly or as clinically necessary, for patients who have been on a stable regimen of Omegaven® for a minimum of 4 months and whose serum bilirubin and hepatic enzymes have normalized.

The study team will round on all inpatients receiving Omegaven® therapy. A complete comprehensive case review for all inpatients receiving Omegaven® therapy under the compassionate-use protocol and any outpatients issues will be discussed among [name], [name], and the study coordinator. All pertinent medical, nutritional, and psychosocial outpatient information will be reviewed during these case reviews.

[name], Department of Surgery, Children's Hospital & Medical Center  
[name], Department of Surgery, Children's Hospital & Medical Center  
[name], Pediatric Research Office, Dept. of Pediatrics, UNMC  
[name], Department of Biostatistics, College of Public Health, UNMC

This study will be monitored by an independent data safety monitoring board (DSMB). The DSMB will have 3 members [[name] (Chair), [name], and [name]]. The Chair will receive copies of all adverse events reports and may call a DSMB meeting based on the reports received. The DSMB will meet formally after the first 4 enrolled subjects and then annually to review preliminary safety data.

*The responsibilities of this board will include:*

- Analysis of the success and safety of the experimental therapy. Success will be measured by each patient's improvement in biochemical markers and avoidance of end stage liver failure.
- Review the research protocol, and amendments, informed consent documents, and plans for data and safety analysis.
- Evaluate the progress of the intervention, including assessment of data quality and timeliness of data entry, participant recruitment, accrual and retention, and any other factors that may affect the study outcome.
- Review any factors external to the study when relevant, such as scientific or therapeutic developments that may have an impact on the safety of the subjects or the ethics of the trial.
- Ensure the confidentiality of the trial data.

The DSMB will be able to contact the investigators at any time by telephone or pager to facilitate adequate feedback of information to medical decision-makers. This will ensure that research felt to involve excessive risk in relation to anticipated benefits is terminated appropriately. To prevent potential or real conflicts of interest, if the research procedure is deemed by the DSMB to involve excessive risk in relation to anticipated benefits, the investigators will be contacted by phone or pager. The research will then be suspended pending further investigation, or terminated at the suggestion of the Board.

